1.2. Sponsor details

Sheffield Teaching Hospitals NHS FT

1.3. Project title

The AspiRATE study: a proof-of-concept assessment of a novel intervention to acoustically detect silent aspiration in patients with acquired dysphagia.

1.4. STH Project Reference number

STH19484

1.5. Protocol version number and date

Version 2.2, October 10th 2017

1.6. Phase of Trial

Phase II: Proof-of-concept diagnostic novel intervention trial

2. Research question

Can silent aspiration during swallowing be reliably detected using acoustic signal processing plus pulse oximetry?

3. Abstract

This proof of concept trial, involving original research from a multicentre, multidisciplinary team, aims to establish whether silent aspiration can be detected in patients with dysphagia (swallowing difficulties), using a microphone array attached to the neck (to capture acoustic respiratory changes), pulse oximetry (to detect reduction in blood oxygen levels) and respiratory rate analysis, with data combined and analysed via post-capture signal processing techniques.

The project aims to develop equipment and signal processing algorithms to a point where a novel intervention has been established that allows semi-automated detection of safe versus unsafe (aspiration) swallows. The intervention will be trialed in patients with dysphagia within standard videofluoroscopy clinics under clinical supervision. There will be ongoing development of the intervention and signal processing algorithms during this process. Public and patient involvement work will feed back into the design process.

If the intervention performs successfully in this proof-of-concept study, we aim to proceed to a larger clinical trial to determine its sensitivity and specificity as a screening tool for aspiration, before final development into a commercial product.

4. Aim of the study

To answer the research question above, with the aim in future project work of developing the technology to ultimately create a semi-automated device to objectively detect silent aspiration in patients with swallowing difficulties.

The ultimate aim of the project is to enable objective, community based assessment of swallow safety for patients who cannot undergo hospital based assessments – for example those with severe cognitive challenges arising from learning difficulties or dementia and those who are bed bound. This would help resolve inequity of access to accurate swallow safety assessment for people with marked physical and/or cognitive challenges, and therefore reduce risks associated with aspiration in these patient groups.

5. Background

Dysphagia (swallowing difficulties) is commonly experienced as a symptom of neurological diseases such as amyotrophic lateral sclerosis (ALS), Parkinson's disease, stroke, dementia, multiple sclerosis (MS) or with traumatic brain injury. Dysphagia is also seen structural or dynamic changes to the caused by head and neck cancer or its treatment. Developmental disorders such as cleft palate, learning difficulty, or cerebral palsy may also cause dysphagia.

Aspiration may occur during dysphagia, whereby food, fluid, saliva or medication penetrates into the airway during swallowing. Aspiration usually triggers a protective cough reflex to clear the material, but in some people this protective mechanism is absent, and they have no indication that they have aspirated: this is called silent aspiration.

Aspiration predisposes to chest infection, which has a significant mortality and morbidity rate. It leads to hospital admissions, longer in-patient episodes, and poorer health outcomes and has been shown to be detrimental to an individual's quality of life.¹⁻⁶ Patients may require modified diet, fluids and medications – or if the dysphagia is severe, they may need feeding by tube. This can result in social isolation and many carers feel guilty eating or drinking in front of patients who are "nil by mouth", treats and social gatherings are affected for all concerned.

It is therefore important to know whether someone is aspirating, as their diet or feeding methods can be changed to reduce the risk of aspiration and its complications.

While aspiration associated with coughing is usually clearly demonstrated by clinical examination by a speech and language therapist or other trained professional, suspected silent aspiration

(penetration of food and/or fluid into the airway without triggering of a cough reflex) is currently detected by one of two instrumental methods.

The first is Fibreoptic Endoscopic Evaluation of Swallowing (FEES), which involves a specialist passing a flexible endoscope down through the nose to directly observe the swallow process. This is time-consuming (taking on average 20 minutes), invasive, and some aspiration can be missed.

Image of FEES Assessment

The second method is video fluoroscopic assessment of swallowing, often considered the 'gold standard'. Videofluoroscopy (VF) requires the patient to swallow a radio-opaque liquid and barium coated solids, allowing a radiographer to follow the liquid/ food's passage through the mouth and pharynx using an x-ray. This investigation has good sensitivity and specificity, but it exposes the patient to radiation, is expensive, requires specialist assessors (usually 2) and can only be done in an appropriate x-ray suite.

Image of VF Assessment

Each of these assessments – while clinically valuable, require the patient to be able to come into hospital, to sit still and to have cognitive capacity to follow instructions. This means that currently they are not available to patients who have significant dementia, learning difficulty or those who are bed bound in the community, creating inequity of care.

A simple, portable screening test for silent aspiration is therefore highly desirable. This would facilitate equity of care and also fit with the care agenda aims of 'taking care to the patient' rather than transporting patients into hospital.

Our innovation and proposed device:

We aim to develop a portable, non-invasive, simple-to-operate and automated device that can be used to screen for silent aspiration. We believe that subtle changes to the breath sounds arising in the trachea and below the vocal cords may indicate if particles of liquid or food have been aspirated.

Similarly, changes in the breathing pattern or percentage blood oxygen saturation may indicate aspiration.

Once fully developed, we envisage that the proposed device would use multiple sensors and advanced signal processing techniques, to give a 'pass/fail' type response for the examiner looking for silent aspiration. We aim for the device sensors to be simple to apply using adhesive pads or a strap.

This study forms the first phase in working towards development of this technology. It builds upon foundation work done by groups using either a single microphone or accelerometers attached to the neck to assess the swallow and breath sounds associated with aspiration. These preliminary studies have provided promising results, but the focus has largely been on sounds heard above the vocal cords, and accuracy of the detection of aspiration has been limited.

The most interesting line of research has been the analysis of lower airway (tracheal) sounds during swallows, with one group reporting an accuracy of 86% for the detection of swallows with silent aspiration⁷. This method aims to detect the end result of aspiration (food or liquid below the vocal cords), and so should have a higher specificity than is found with other techniques.

Pulse oximetry has also shown some potential as a measure of silent aspiration, but current consensus in the literature is that, while it has value as an adjunctive measure, it is not sufficiently reliable for use in isolation⁸.

The unique element to our work is a multi-channel approach using an array of microphones, and sophisticated processing of the audio and other sensor outputs. We will start by recording swallow and tracheal sounds via multiple microphones, in conjunction with pulse oximetry. Signal processing experts within the team will pick out characteristic signals associated with the normal swallow and episodes of aspiration. Through the development process we will narrow down the minimum set of sensors required to optimise test sensitivity and specificity. It may be that multiple measurements of the same type (sounds) or a mixture of measurement types (sounds and pulse oximetry) will give us the most information. We believe the microphone array and multi-channel analysis design can be superior in sensitivity and specificity when compared to existing reported techniques⁷.

PPI evaluation will be undertaken to explore the acceptability/tolerability of wearing the equipment array, and also the potential perceived benefits of access in the community to objective swallow safety assessment, particularly for groups previously excluded by cognitive or physical challenges. Sheffield Teaching Hospitals NHS FT has access to a database of patients and carers who have previous or ongoing experience of swallowing problems, and who have agreed to act as reviewers for studies. A focus group consisting of these individuals will be arranged by letter of invitation.

A robust prototype will be designed and manufactured collaboratively by Sheffield Teaching Hospitals NHS FT and Cambridge University, to incorporate the final set of sensors and analysis software. The aim is for this equipment array to be approved for research use in patients, and assessed in a proof of concept trial.

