6.5. Sample size

The aim of the current work is not to establish diagnostic accuracy of the equipment array, but rather to develop the hardware and processing algorithms for use in a future larger clinical trial.

Based on experience from similar projects, a sample size of 20 - 45 has been chosen for Part 2 of the study, with an intention to recruit the 3 patient groups described above, aiming for up to 5 - 15 in each group but with the understanding that targets will be subject to referral patterns within the study timescale.

We will not know which groups patients will fall into before testing, and so consecutive cases will be approached and consented for the trial. After recording from the device and analysis of the videofluoroscopy examination, patients will be allocated to one of the three groups. Data collection will continue until all either: a) each group has recruited 15 participants or b) recruitment time for the study is ended and data recorded from extra cases in already completed groups will still be entered into the analysis.

Age and sex matching will not be used, as is standard practice in this early stage of proof-of-principle research.

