6.7. Outcome measure(s)

As a proof-of-concept study the outcomes of interest are primarily qualitative: feasibility of the use of the equipment array, characteristics of acoustic signals from cases and controls, equipment safety and patient group feedback.

No statistical comparisons will be drawn between the case-control groups identified by the equipment array. A future clinical study will establish sensitivity and specificity of the equipment array as a device for the detection of aspiration, with reference to videofluoroscopy. This will be powered for the primary outcome of diagnostic accuracy.

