6.8. Analysis including statistical methods

[figure not shown]
Anonymized data (from both the equipment array and the videofluoroscopy) will be examined by the research team. Standard methods of analysis will be applied to acoustic recordings to assess the differences between those from aspirating and non-aspirating patients, and to compare these findings with the aspirating and non-aspirating videofluoroscopy data. An auditory processing algorithm that can be applied to future recordings will be developed.

Data from the device (index test) and videofluoroscopy (reference standard) will be used to populate a standard 2x2 table, allowing calculation of the device sensitivity and specificity. Receiver Operating Characteristic (ROC) curve analysis will allow refinement of the signal processing algorithm and interpretation thresholds, although as a screening test false positives will be considered preferable false negatives.

[figure not shown]
6.9. Intervention:

Patient Pathways

Part 1 Trial

Part 2 Trial

Flow chart indicating participant's involvement throughout the course of the study

6.10. Safety assessment:

The following issues have been considered as part of the risk assessment process of the new equipment array.

- Device obscures visualization of swallow on videofluoroscopy due to inadequate radiolucency – Videofluoroscopy assessments will be conducted by speech and language and radiography professionals, and initial testing (part 1 trial) includes built-in time to allow

the device to be adjusted or modified to improve videofluoroscopy views. In individual patients testing will be terminated early if inadequate views can be obtained for clinical use.

- Equipment prevents adequate patient positioning for videofluoroscopy – The attachment of the equipment attachment will be designed in conjunction with Speech and Language Therapists ensuring that it should not prevent the expected patient positioning. Initial PPI and the Part 1 trial are designed to allow refinement of the design if positioning proves problematic. In individual patients testing will be terminated early if positioning is inadequate for clinical use.

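### Sections 2 and 4 set the study to answer whether silent aspiration is reliably detected, while 6.5 and 6.7 disclaim accuracy and 6.8 calculates it without calling it developmental

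*Protocol*

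**What the plan says.** Protocol section 2 poses the research question: "Can silent aspiration during swallowing be reliably detected using acoustic signal processing plus pulse oximetry". Section 4 adopts it as the aim of the present study: "To answer the research question above, with the aim in future project work of developing the technology". Only the device development in the second half of that sentence is put off to later work. *Reliably* is not defined anywhere.

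Three later sections describe the study differently:

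- Section 6.5: "The aim of the current work is not to establish diagnostic accuracy of the equipment array". The purpose given instead is developing the hardware and the processing algorithms.
- Section 6.7: "As a proof-of-concept study the outcomes of interest are primarily qualitative". No statistical comparison between groups is planned, and accuracy is deferred: "A future clinical study will establish sensitivity and specificity of the equipment array as a device for the detection of aspiration".
- Section 6.8: index test and reference standard are cross-classified in a 2x2 table, "allowing calculation of the device sensitivity and specificity". ROC analysis is used to refine the algorithm and its cut-offs. No separate validation data are described.

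Section 6.5 gives 20-45 patients for Part 2, with up to 5-15 in each of three groups, silent aspiration being one. The targets depend on referrals, and extra cases in a full group are still analysed.

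**The concern.** Whether a test reliably detects a condition, judged against videofluoroscopy, is a question of diagnostic accuracy. The protocol therefore states an aim in sections 2 and 4 that 6.5 and 6.7 disclaim. An author reporting the study has two incompatible statements of what it was for.

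Section 6.8 makes this matter in practice. It will produce a sensitivity and a specificity that look like an answer to section 2, with nothing in the protocol marking them as by-products of development. Because thresholds are refined on the same patients, those figures would tend to flatter the device. With no criterion for *reliably* and few silent aspirators, a publication could claim reliable detection, or its absence, from data compatible with both.

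**Working it through.** **1. The statements side by side**

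| Protocol section | What it commits to |
|---|---|
| 2 and 4 | This study answers whether detection is reliable |
| 6.5 | Establishing accuracy is not the aim; development is |
| 6.7 | Outcomes mainly qualitative; sensitivity and specificity come from a future study |
| 6.8 | Sensitivity, specificity and ROC calculated in this study |
| 3 (abstract) and 13 | Accuracy belongs to a later, larger trial |

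The firm conflict is between sections 2 and 4 on one side and 6.5 and 6.7 on the other. Section 6.8 adds to it.

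**2. Inputs for the size of the problem**

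- Silent-aspiration group: up to 5-15 (section 6.5), a soft target.
- Reference value for sensitivity: 91%, from the single-microphone study cited in section 5.2.
- Denominator: silent aspirators, one result per patient. This is an assumption, made because section 2 asks about silent aspiration. Section 6.8 contrasts aspirating with non-aspirating patients, so a pooled figure is shown as well.
- The 20-45 is said to rest on experience. No power, precision or target accuracy is given, so there is no calculation to reproduce.

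**3. Exact (Clopper-Pearson) 95% intervals for x detected out of n**

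Lower limit = Beta quantile at 0.025 with parameters (x, n-x+1). Upper limit = Beta quantile at 0.975 with parameters (x+1, n-x). When x = n, the lower limit is 0.025^(1/n) and the upper limit is 1.

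- 0.025^(1/5) = 0.478
- 0.025^(1/15) = 0.782

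| Detected | Estimate | 95% CI |
|---|---|---|
| 4/5 | 80.0% | 28.4-99.5% |
| 5/5 | 100% | 47.8-100% |
| 9/10 | 90.0% | 55.5-99.7% |
| 13/15 | 86.7% | 59.5-98.3% |
| 14/15 | 93.3% | 68.1-99.8% |
| 15/15 | 100% | 78.2-100% |
| 27/30, both aspirating groups pooled | 90.0% | 73.5-97.9% |

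**4. What could be shown at one-sided 0.025**

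The benchmarks of 50%, 70% and 80% are assumptions.

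- n = 5: 0.5^5 = 0.031, above 0.025. Even 5/5 does not exclude a sensitivity of 50%.
- n = 15, benchmark 70%: only 15/15 suffices (0.7^15 = 0.0047). If true sensitivity is 91%, the chance of 15/15 is 0.91^15 = 0.243.
- n = 15, benchmark 80%: 0.8^15 = 0.035, above 0.025, so no result suffices.
- n = 15, benchmark 50%: 12/15 or better suffices, with power 96% at a true 91%.

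**5. Numbers needed for precision (normal approximation, assumed targets)**

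n = 1.96² × 0.91 × 0.09 / h². For h = 0.10 this is 31.5, so 32 silent aspirators. For h = 0.05 it is 125.9, so 126.

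**6. Direction of bias**

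These intervals treat the classification rule as fixed in advance. Section 6.8 refines it on the data being summarised, so the estimates would tend to be too high and the intervals do not allow for that.

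**The case against.** The strongest reply is that the protocol is candid about its limits. The abstract and sections 6.5, 6.7 and 13 all leave accuracy to a later trial. Section 13 makes going forward depend only on some ability to discriminate, and no decision hangs on the word *reliably*. A descriptive 2x2 table and ROC curve are normal tools for building an algorithm and are compatible with not establishing accuracy. Most of this stands. It means that 6.8 alone is not a contradiction and that the sample size is not at fault. It does not reconcile sections 2 and 4 with 6.5 and 6.7, and a SAP cannot settle which aim the protocol has.

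A second reply is that the silent-only denominator is too harsh. Pooling both aspirating groups would give about 10-30 positives at target, and counting swallows would give more observations. That is fair as a reading of 6.8, and section 6.1 does compare swallows. But pooling answers a different question from section 2, 27/30 still leaves a lower limit of 73.5%, and swallows are clustered within patients.

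Two stronger readings are tempting and not supported:

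- A reader might infer that the protocol itself says its design cannot answer the research question. It says only that establishing accuracy is not the aim.
- A reader might fault 6.8 for not asking for confidence intervals. That is ordinary SAP detail, and the SAP is not at hand.

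**Conclusion.** The concern holds as a conflict in the stated aims: sections 2 and 4 promise an answer on reliable detection, 6.5 and 6.7 disclaim it, and 6.8 supplies unlabelled figures from tuning data that could be taken for that answer. At the planned group size, even perfect detection leaves a lower 95% limit of 47.8% with 5 silent aspirators and 78.2% with 15.

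This size rests on a silent-only, patient-level denominator and on a soft target: fewer than 5 or more than 15 are both possible. Any judgement that these limits are too low for screening also needs a threshold, which the protocol does not give. A reader might conclude that the study is too small. For developing hardware and an algorithm the documents do not support that. What cannot be delivered is the question as worded. The remedy is worth making because it changes what the report may conclude, at little cost.

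**What to change.** - **Sections 2 and 4:** restate the question as what 6.5, 6.7 and 13 describe: whether array and oximetry recordings show features that separate aspirating swallows (silent ones included) from non-aspirating swallows well enough to build an algorithm for a later accuracy trial. Keep the wording descriptive, so that it agrees with the statement in 6.7 that groups will not be compared statistically.
- **Sections 6.7 and 6.8:** say that sensitivity, specificity and ROC results are apparent, development-stage estimates from the data used for tuning, and that no conclusion on reliable detection will be drawn from them.
- **If intervals are reported:** allow for clustering of swallows within patients, and state that the intervals do not correct for optimism. Alternatively, take the estimates from cross-validation that leaves out whole patients. A plain exact interval on tuned data would look more trustworthy than it is.

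Cost: wording in four sections, a little more analysis work and a less favourable headline claim. Sample size and recruitment do not change.

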5.1. Clinical significance

Patients and healthcare in general

Dysphagia and aspiration are common disorders, but with up to 59% of these patients suffering from silent aspiration, it can be difficult to detect^{9, 10, 11}. If recognised, dietary modifications and swallowing strategies can be used to limit the condition's associated morbidity and mortality.

A common cause of dysphagia and silent aspiration is stroke⁶. In the acute phase after a stroke, the incidence of silent aspiration can be as high as 67%⁹, and for many patients, aspiration then persists into the rehabilitation stage. Aspiration is strongly associated with an increased risk of

developing chest infection, and many stroke patients require dietary modification, or in some cases feeding tubes.

Aspiration is also seen in association with a wide range of other conditions such as neurodegenerative disorders (e.g. multiple sclerosis, Parkinson's disease) and vocal cord palsy¹². It may also be caused by medical interventions, such as the treatment of nasopharyngeal, laryngeal and oral cancer^{13,14}.

Bedside investigations for dysphagia are available (such as the water provocation test¹⁵), though a recent systematic review concluded "although a wide variety of screening and assessment tests are available for use, none have acceptable sensitivity and specificity to ensure accurate detection of dysphagia"¹¹. The detection of *silent* aspiration with these methods is almost impossible.

Currently, aspiration is diagnosed through FEES or videofluoroscopy, both of which require skilled staff, usually working in a hospital clinic that may only run weekly. For this reason, and due to the associated costs (videofluoroscopy costs the NHS £231 per test), these more accurate investigations are not available to all people presenting with dysphagia. Some hospitals do not have access to videofluoroscopy and need to transport patients out of district to a hospital which has this service.

Our proposed approach could revolutionise the way that dysphagia and aspiration are managed. A quick, automated screening test would allow any individual with basic training to test a patient with suspected aspiration at any time. In particular, regular non-specialist re-assessment would become possible, as would screening and testing in difficult circumstances. This would facilitate best ongoing management of oral intake and associated timely referrals to therapy and dietetic services.

